9.65 Pulmonary Events Including Pneumonitis

Mild to moderate events of pneumonitis have been reported with atezolizumab and cobimetinib. Pulmonary events may present as new or worsening cough, chest pain, fever, dyspnea, fatigue, hypoxia, pneumonitis, and pulmonary infiltrates. Patients should be assessed for pulmonary signs and symptoms throughout the study and have computed tomography (CT) scans of the chest performed as clinically indicated.

All pulmonary events should be thoroughly evaluated for other commonly reported etiologies such as pneumonia/infection, lymphangitic carcinomatosis, pulmonary embolism, heart failure, chronic obstructive pulmonary disease, or pulmonary hypertension. For events of pneumonitis, consider comprehensive infectious evaluation including viral etiologies.

- 9.651 Grade 1: No change in treatment  
Monitor closely  
Re-evaluate on serial imaging  
Consider referral to pulmonary specialist
- 9.652 Grade 2:  
Refer patient to pulmonary and infectious disease specialists and consider bronchoscopy or BAL with or without transbronchial biopsy  
Initiate steroids at 1-2 mg/kg/day of prednisone or equivalent.
- 9.653 Grade 3 or greater:  
Oral or IV broad-spectrum antibiotics should be administered in parallel to the immunosuppressive treatment.  
Bronchoscopy or BAL with or without transbronchial biopsy is recommended.  
Initiate treatment with corticosteroids equivalent to 1-2 mg/kg/day IV methylprednisolone.  
If event does not improve within 48 hours after initiating corticosteroids, consider adding an immunosuppressive agent.

9.66 Liver Dysfunction

- 9.661 For patients without hepatocellular carcinoma (HCC) any hepatic event:  
Grade 1: Monitor LFTs until values resolve to within normal limits or to baseline values  
Grade 2:  
All events - Monitor LFTs more frequently until values resolve to baseline values  
Events of >5 days' duration:  
Initiate treatment with corticosteroids equivalent to 1-2 mg/kg/day oral prednisone  
Grade 3 or 4:  
Consider patient referral to gastrointestinal specialist for evaluation and liver biopsy to establish etiology of hepatic injury.  
Initiate treatment with corticosteroids equivalent to 1-2 mg/kg/day oral prednisone.  
If event does not improve within 48 hours after initiating corticosteroids, consider adding an immunosuppressive agent.  
If event resolves to Grade 1 or better, taper corticosteroids over  $\geq 1$  month.
- 9.662 For patients with hepatocellular carcinoma (HCC):
  - 9.6621 If any of the following are true:
    - AST/ALT is within normal limits at baseline and increases to  $> 3 \times \text{ULN}$  to  $\leq 10 \times \text{ULN}$
    - or**

AST/ALT is  $> \text{ULN}$  to  $\leq 3 \times \text{ULN}$  at baseline and increases to  $> 5 \times \text{ULN}$  to  $\leq 10 \times \text{ULN}$

**or**

AST/ALT is  $> 3 \times \text{ULN}$  to  $\leq 5 \times \text{ULN}$  at baseline and increases to  $> 8 \times \text{ULN}$  to  $\leq 10 \times \text{ULN}$

Then:

Monitor LFTs more frequently until resolution to baseline values

For events of  $> 5$  days' duration:

Consider initiating systemic steroid therapy at 1-2 mg/kg/day of prednisone or equivalent.

9.6622 AST or ALT  $> 10 \times \text{ULN}$  or bilirubin  $> 3 \times \text{ULN}$ :

Initiate treatment with equivalent to 1-2 mg/kg/day oral prednisone.

If no improvement within 48 hours consider addition of immunosuppressive agent.

If event resolves to baseline, taper corticosteroids over  $\geq 1$  month.

9.67 Pancreatitis and Amylase/Lipase elevations

The differential diagnosis of acute abdominal pain should include pancreatitis. Appropriate workup should include an evaluation for ductal obstruction, as well as serum amylase and lipase tests.

9.671 Elevations Grade 2 – prolonged elevations  $> 3$  weeks consider 10 mg/day oral prednisone or equivalent. Monitor amylase/lipase weekly.

9.672 Elevations Grade  $\geq 3$  – Refer patient to GI specialist. Monitor amylase/lipase every other day. If no improvement, consider treatment with corticosteroids equivalent 1-2 mg/kg/day oral prednisone.

9.673 Immune-mediated pancreatitis Grade 2 or 3 – Refer patient to GI specialist. Initiate treatment with corticosteroids equivalent to 1-2 mg/kg/day IV methylprednisolone and convert to 1-2 mg/kg/day oral prednisone or equivalent upon improvement

9.674 Immune-mediated pancreatitis Grade 4 – Refer patient to GI specialist. Initiate treatment with corticosteroids equivalent to 1-2 mg/kg/day IV methylprednisolone and convert to 1-2 mg/kg/day oral prednisone or equivalent upon improvement. If event does not improve within 48 hours after initiating corticosteroids, consider adding an immunosuppressive agent. If event resolves to Grade 1 or better, taper corticosteroids over  $\geq 1$  month.

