	Retinopathy (serous retinopathy, chorioretinopathy) or Retinal detachment (RPED) Grade 2-3	Omit until $\leq$ Grade 1 Resume at same dose once $\leq$ Grade 1	Omit until $\leq$ Grade 1 Resume at dose reduced by 1 level once $\leq$ Grade 1	Continue
	Grade 4	Omit until $\leq$ Grade 1 Resume with dose reduced by 1 level once $\leq$ Grade 1	Discontinue	Continue
Eye disorders (refer to Ophthalmology)	Retinal vascular disorder (Retinal Vein Occlusion) (Any grade)	Discontinue	Discontinue	Continue
Gastrointestinal disorders	Diarrhea/Colitis Grade 2	Omit until symptoms resolve to $\leq$ Grade 1 For Grade 2 may resume previous dose level	Omit until symptoms resolve to $\leq$ Grade 1 Resume at one dose level lower	Omit and resume when symptoms resolve to $\leq$ Grade 1,
	Grade 3	Omit until symptoms resolve to $\leq$ Grade 1 Resume at one dose level lower	Omit until symptoms resolve to $\leq$ Grade 1 Resume at one dose level lower	Omit and resume when symptoms resolve to $\leq$ Grade 1
	Grade 4	Discontinue	Discontinue	Discontinue
	Pancreatitis (amylase/lipase increased) Grade 2	Continue	Continue	Continue at provider's discretion Monitor amylase/lipase weekly See Section 9.0
	Grade 3	Omit until $\leq$ Grade 2 Resume with dose reduced by 1 levels once $\leq$ Grade 2	Omit until $\leq$ Grade 2 Resume with dose reduced by 1 levels once $\leq$ Grade 2	Omit until $\leq$ Grade 2 Initiate supportive care per Section 9.0 Resume once symptoms resolve to $\leq$ Grade 2 If pancreatitis recurs, permanently discontinue atezolizumab

CTCAE System/Organ/Class (SOC)	ADVERSE EVENTS/SYMPTOMS	ACTIONS		
		Vemurafenib (BRAF-mutant only)	Cobimetinib	Atezolizumab (All patients)
	Grade 4	Omit until $\leq$ Grade 2 Resume with dose reduced by 1 levels once $\leq$ Grade 2	Omit until $\leq$ Grade 2 Resume with dose reduced by 1 levels once $\leq$ Grade 2	Discontinue
General disorders and administration site conditions	Infusion-related reaction Grade $\geq 3$	Continue	BRAFm – Continue BRAFWt – Discontinue	Discontinue
Immune System Disorders	Allergic reaction or Anaphylaxis Grade 2	Continue	Continue	Omit and resume when symptoms resolve to $\leq$ Grade 1 Pre-treatment required prior to subsequent doses Resume at same dose
	Grade $\geq 3$	Discontinue	Discontinue	Discontinue

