	Grade 3	Omit and resume when symptoms resolve to $\leq$ Grade 1	Omit and resume when symptoms resolve to $\leq$ Grade 1
Gastrointestinal disorders	Grade 4	Discontinue	Discontinue
	Pancreatitis (amylase/lipase increased) Grade 2	Continue at provider's discretion Monitor amylase/lipase weekly See Section 9.0	Continue at provider's discretion Monitor amylase/lipase weekly See Section 9.0
	Grade 3	Omit until $\leq$ Grade 2 Initiate supportive care per Section 9.0 Resume once symptoms resolve to $\leq$ Grade 2 If pancreatitis recurs, permanently discontinue	Omit until $\leq$ Grade 2 Initiate supportive care per Section 9.0 Resume once symptoms resolve to $\leq$ Grade 2 If pancreatitis recurs, permanently discontinue atezolizumab
	Grade 4	Discontinue	Discontinue
General disorders and administration site conditions	Infusion-related reaction Grade $\geq 3$	Discontinue See Section 9.0	Discontinue See Section 9.0
Immune system disorders	Allergic reaction or Anaphylaxis Grade 2	Omit and resume when symptoms resolve to $\leq$ Grade 1 Pre-treatment required prior to subsequent doses Resume at same dose	Omit and resume when symptoms resolve to $\leq$ Grade 1 Pre-treatment required prior to subsequent doses Resume at same dose
	Grade $\geq 3$	Discontinue	Discontinue

CTCAE System/Organ/Class (SOC)	ADVERSE EVENTS/SYMPTOMS	ACTIONS	
		Tiragolumab	Atezolizumab
Immune system disorders	Cytokine release syndrome Grade $\geq 3$ per CTCAE v 5.0	Discontinue if CRS due to tiragolumab See Section 9.7	Discontinue if CRS due to atezolizumab See Section 9.7
Immune system disorders	Immune System Disorders, Other: Hemophagocytic lymphohistiocytosis (HLH) and macrophage activation syndrome (MAS)	Discontinue See Section 9.0	Discontinue See Section 9.0
Immune system disorders	Immune System Disorders, Other: Immune-related myasthenic syndrome/myasthenia gravis, Guillain-Barré or meningoencephalitis	Permanently discontinue tiragolumab	Permanently discontinue atezolizumab
Investigations	Aspartate aminotransferase or Alanine aminotransferase increased Grade 1	Continue, but monitor LFTs weekly	Continue, but monitor LFTs weekly
	Grade 2 (AST/ALT $>3.0$ - $5.0$ x ULN)	Omit treatment Monitor LFTs weekly Resume when symptoms resolve to $\leq$ Grade 1	Omit treatment Monitor LFTs weekly Resume when symptoms resolve to $\leq$ Grade 1

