	Grade 3 (AST/ALT $>5.0$ - $10.0$ x ULN)	Omit and initiate systemic steroid treatment (see Section 9.0) Consult Hepatology if not improving within 1 week Resume when symptoms resolve to $\leq$ Grade 1	Omit and initiate systemic steroid treatment (see Section 9.0) Consult Hepatology if not improving within 1 week Resume when symptoms resolve to $\leq$ Grade 1
	Grade 3+ (AST/ALT $>10.0$ x ULN)	Discontinue Consult Hepatology	Discontinue Consult Hepatology
Investigations	Blood bilirubin increased Total bilirubin $>2$ x ULN For patients with Gilbert's syndrome: modify dose only if direct bilirubin is $>2$ x ULN	Discontinue Consult Hepatology	Discontinue Consult Hepatology
Investigations	Lymphocyte count decreased Grade 4	Omit until $\leq$ Grade 2 Resume once $\leq$ Grade 2	Omit until $\leq$ Grade 2 Resume once $\leq$ Grade 2
Renal and urinary disorders	Acute kidney injury Grade 2	Omit until $\leq$ Grade 1 Resume when symptoms resolve to $\leq$ Grade 1	Omit until $\leq$ Grade 1 Resume when symptoms resolve to $\leq$ Grade 1

CTCAE System/Organ/Class (SOC)	ADVERSE EVENTS/SYMPTOMS	ACTIONS	
		Tiragolumab	Atezolizumab
Renal and urinary disorders	Grade $\geq 3$	Discontinue	Discontinue
Respiratory, thoracic and mediastinal disorders	Pneumonitis Grade 2	Omit until $\leq$ Grade 1 Resume once symptoms resolve to $\leq$ Grade 1	Omit until $\leq$ Grade 1 Resume once symptoms resolve to $\leq$ Grade 1
	Grade $\geq 3$	Discontinue	Discontinue
Skin and subcutaneous tissue disorders	Erythema multiforme Grade $\geq 3$	Omit and initiate supportive care per Section 9.0 Refer to Dermatology	Omit and initiate supportive care per Section 9.0 Refer to Dermatology
Skin and subcutaneous tissue disorders	Rash acneiform Grade 2	Continue Initiate supportive care per Section 9.0 Refer to Dermatology if does not improve to $\leq$ Grade 1 within 2 weeks	Continue Initiate supportive care per Section 9.0 Refer to Dermatology if does not improve to $\leq$ Grade 1 within 2 weeks
	Grade 3	Omit and initiate supportive care per Section 9.0 Refer to Dermatology Resume once $\leq$ Grade 1	Omit and initiate supportive care per Section 9.0 Refer to Dermatology Resume once $\leq$ Grade 1
	Grade 4	Omit and initiate supportive care per Section 9.0 Refer to Dermatology Resume once $\leq$ Grade 1	Omit and initiate supportive care per Section 9.0 Refer to Dermatology Resume once $\leq$ Grade 1

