Skin and subcutaneous tissue disorders	Rash maculo-papular Grade 2	Continue Initiate supportive care per Section 9.0 Refer to Dermatology if does not improve to $\leq$ Grade 1 within 2 weeks	Continue Initiate supportive care per Section 9.0 Refer to Dermatology if does not improve to $\leq$ Grade 1 within 2 weeks
	Grade 3	Omit and initiate supportive care per Section 9.0 Refer to Dermatology Resume when symptoms resolve to $\leq$ Grade 1	Omit and initiate supportive care per Section 9.0 Refer to Dermatology Resume when symptoms resolve to $\leq$ Grade 1
	Grade 4	Discontinue	Discontinue
Skin and subcutaneous tissue disorders	Stevens-Johnson syndrome $\geq$ Grade 3	Discontinue and initiate supportive care per Section 9.0 Refer to Dermatology	Discontinue and initiate supportive care per Section 9.0 Refer to Dermatology

CTCAE System/Organ/Class (SOC)	ADVERSE EVENTS/SYMPTOMS	ACTIONS	
		Tiragolumab	Atezolizumab
Skin and subcutaneous tissue disorder	Toxic epidermal necrolysis (TEN) Grade 4	Discontinue and initiate supportive care per Section 9.0 Refer to Dermatology	Discontinue and initiate supportive care per Section 9.0 Refer to Dermatology
Skin and subcutaneous tissue disorder	Skin and subcutaneous tissue disorder – Other Drug rash with eosinophilia and systemic symptoms (DRESS)	Discontinue and initiate supportive care per Section 9.0 Refer to Dermatology	Discontinue and initiate supportive care per Section 9.0 Refer to Dermatology
Other Adverse Events	Grade 3	Omit until $\leq$ Grade 1 Resume once symptoms resolve to $\leq$ Grade 1	Omit until $\leq$ Grade 1 Resume once symptoms resolve to $\leq$ Grade 1
	Grade 4	Discontinue	Discontinue

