CTCAE System/Organ/Class (SOC)	ADVERSE EVENTS/SYMPTOMS	Atezolizumab
Gastrointestinal Disorders	Diarrhea/Colitis Grade 2	Withhold atezolizumab for up to 12 weeks after event onset (a) See Section 9.0 for suggested supportive care If event resolves to Grade 1 or better, resume atezolizumab (b) If event does not resolve to Grade 1 or better while withholding atezolizumab, permanently discontinue atezolizumab (c)
	Grade 3	Withhold atezolizumab for up to 12 weeks after event onset (a) If event resolves to Grade 1 or better, resume atezolizumab (b) If event does not resolve to Grade 1 or better while withholding atezolizumab, permanently discontinue atezolizumab (c)
	Grade 4	Permanently discontinue atezolizumab
Gastrointestinal disorders	Pancreatitis (immune-mediated) Grade 2 or 3	Withhold atezolizumab for up to 12 weeks after event onset (a) If event resolves to Grade 1 or better, resume atezolizumab (b) If event does not resolve to Grade 1 or better while withholding atezolizumab, permanently discontinue atezolizumab (c) For recurrent events, permanently discontinue atezolizumab (See Investigations/Lipase increased or serum amylase increased below)
	Grade 4	Permanently discontinue atezolizumab
General disorders and administration site conditions	Infusion-related reaction Grade 3-4	Discontinue
Infections and infestations	Myelitis, immune-mediated Grade 2-4	Permanently discontinue atezolizumab See Section 9.0 for suggested supportive care
Immune system disorders	Allergic reaction or Anaphylaxis Grade 2	Hold and resume when symptoms resolve to ≤Grade 1 Pre-treatment required prior to subsequent doses (Section 9.0)
	Grade 3-4	Discontinue
Immune system disorders	Immune system disorders, other (specify): Immune-related myasthenic syndrome/myasthenia gravis, Guillain-Barré, or meningoencephalitis	Permanently discontinue atezolizumab

CTCAE System/Organ/Class (SOC)	ADVERSE EVENTS/SYMPTOMS	Atezolizumab
Investigations For patients without hepatocellular carcinoma (HCC)	Aspartate aminotransferase increased or Alanine aminotransferase increased or Blood bilirubin increased Grade 1	Continue, and monitor LFTs more frequently until return to baseline values

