	Grade 2	Monitor LFTs more frequently until return to baseline values For events lasting >5 days Withhold atezolizumab for up to 12 weeks after event onset (a) See Section 9.0 for suggested supportive care Resume if event resolves to ≤Grade 1 (b) If event does not resolve to Grade 1 or better while withholding atezolizumab, permanently discontinue atezolizumab (c)
	Grade 3-4	Permanently discontinue atezolizumab See Section 9.0 for suggested supportive care
	Aspartate aminotransferase increased or Alanine aminotransferase increased If within normal limits at baseline and increases to ≥Grade 1	Withhold atezolizumab for up to 12 weeks after event onset (a) Monitor LFTs more frequently until return to baseline values If event resolves to baseline or to Grade 1 or better, resume atezolizumab (b) If event does not resolve to baseline or to Grade 1 or better while withholding atezolizumab, permanently discontinue atezolizumab (c)
Investigations For patients with hepatocellular carcinoma (HCC)	Aspartate aminotransferase increased or Alanine aminotransferase increased >10 x ULN or Blood bilirubin increased Total bilirubin >3 x ULN	Permanently discontinue atezolizumab See Section 9.6 for suggested supportive care
	Lipase increased or Serum amylase increased Grade 2 (>1.5-2.0 x ULN)	Continue atezolizumab
	Grade 3 (>2.0- 5.0 x ULN)	Withhold atezolizumab for up to 12 weeks after event onset (a) If event resolves to Grade 1 or better, resume atezolizumab If event does not resolve to Grade 1 or better while withholding atezolizumab, permanently discontinue atezolizumab For recurrent events, permanently discontinue atezolizumab (c)
Renal and urinary disorders	Acute kidney injury Grade 2	Withhold atezolizumab for up to 12 weeks after event onset If event resolves to Grade 1 or better, resume atezolizumab (b) If event does not resolve to Grade 1 or better while withholding atezolizumab, permanently discontinue atezolizumab (c)
	Grade 3-4	Permanently discontinue atezolizumab

CTCAE System/Organ/Class (SOC)	ADVERSE EVENTS/SYMPTOMS	Atezolizumab
Respiratory, thoracic and mediastinal disorders	Pneumonitis Grade 1	Continue atezolizumab and monitor closely For Grade 1 pneumonitis, consider withholding atezolizumab

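### In Arm C, the binding Table 8.22 lets both antibodies continue at Grade 2 immune-mediated pancreatitis and restart at Grade 2 after Grade 3, and the safeguards elsewhere cover this only in part

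*Combined protocol and SAP*

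**What the plan says.** Table 8.22 governs both antibodies in the Arm C neoadjuvant phase. Its pancreatitis row carries amylase and lipase increase in the same label and gives both drugs the same actions. At Grade 2 it reads "Continue at provider's discretion Monitor amylase/lipase weekly See Section 9.0". At Grade 3 both drugs are omitted with supportive care under Section 9.0, and then: "Resume once symptoms resolve to $\leq$ Grade 2 If pancreatitis recurs, permanently discontinue". Grade 4 means discontinuation.

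Two other places keep the conditions apart. Sections 9.671 and 9.672 deal with enzyme elevation; 9.673 and 9.674 deal with immune-mediated pancreatitis. For the latter, 9.673 says: "Immune-mediated pancreatitis Grade 2 or 3 – Refer patient to GI specialist. Initiate treatment with corticosteroids equivalent to 1-2 mg/kg/day IV methylprednisolone". The adjuvant Table 8.3, which covers atezolizumab only, has its own Grade 2-3 row for the immune-mediated disease, which directs: "Withhold atezolizumab for up to 12 weeks after event onset (a) If event resolves to Grade 1 or better, resume atezolizumab (b". Notes (a) and (b) there concern the steroid taper.

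The texts differ in force. Section 8.0 says the neoadjuvant modifications are to be followed strictly and the adjuvant ones treated as guidelines. Section 9.6 describes itself as guidance.

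**The concern.** The phase that gives two checkpoint antibodies has the looser rule for immune-mediated pancreatitis, and that rule sits in the table sites must follow. A site can comply with Table 8.22 and still give both drugs at the grade where Section 9.673 starts intravenous steroids. After a Grade 3 event, the table's own condition for restarting both drugs is met while the patient is still at Grade 2. Pancreatitis is listed in Section 10.561 as an adverse event of special interest for these drugs. What is at stake is patient safety and uniform handling across sites, more than the pathologic complete response (pCR) estimate.

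**Working it through.** No figure in the plan is in dispute, so the main check is a comparison of texts. The arithmetic follows it.

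**1. Immune-mediated pancreatitis in three places**

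| | Table 8.22 (strict, both drugs) | Section 9.673 (guideline) | Table 8.3 (guideline, atezolizumab) |
|---|---|---|---|
| Grade 2 | Left to the provider | IV steroids, 1-2 mg/kg/day | Withhold |
| Grade 3 | Omit | Same steroids | Withhold |
| Restart | Grade 2 or lower | Not addressed | Grade 1 or better |

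**2. The row within its own table**

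- *Rows of Table 8.22 with a Grade 2 action.* Eight hold both drugs: adrenal insufficiency, hyperthyroidism, eye, diarrhea/colitis, allergic reaction, AST/ALT, acute kidney injury and pneumonitis. Three do not: pancreatitis and the two rash rows. 8 + 3 = 11.
- *Rows that restart both drugs at a stated grade after Grade 3.* Seven require Grade 1 or lower: adrenal insufficiency, hyperthyroidism, diarrhea/colitis, AST/ALT, acneiform rash, maculo-papular rash and the default for unlisted events. Pancreatitis alone allows Grade 2. 7 + 1 = 8.
- *Not counted.* Hyperglycemia and erythema multiforme state no restart grade, hypophysitis states no event grade, and for eye events atezolizumab is stopped.

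The default for an unlisted Grade 3 event is "Omit until $\leq$ Grade 1 Resume once symptoms resolve to $\leq$ Grade 1", so an unlisted event meets a tighter rule than pancreatitis does. The only other Grade 2 restart is for lymphocyte count after Grade 4, a laboratory finding: "Omit until $\leq$ Grade 2 Resume once $\leq$ Grade 2". The atezolizumab cell for the closed Arms A and B in Table 8.21 reads "Omit until $\leq$ Grade 2 Initiate supportive care per Section 9.0 Resume once symptoms resolve to $\leq$ Grade 2", so the row may have been carried over. No rationale is given.

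**3. Other Grade 2 events treated with the same steroid dose**

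Section 9.6 also gives 1-2 mg/kg/day at Grade 2 for pneumonitis (9.652), renal events (9.69d), hepatic events lasting more than 5 days (9.661) and recurrent or persistent colitis (9.612). The matching Table 8.22 row omits both drugs at Grade 2 in all four. Among the rows with a Grade 2 action, only pancreatitis combines that steroid dose with permission to keep dosing.

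**4. How far the safeguards reach**

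- Section 8.2 permits a provider to hold a dose but does not require it.
- Section 8.13 requires a taper over at least 1 month to 10 mg/day or less. It applies only once a drug is withheld, sets no event grade, and names only atezolizumab for resumption.
- The Table 8.22 preamble recommends delaying both drugs together.
- Section 9.673 gives no dosing instruction, and Section 9.51 sends dosing decisions back to Sections 8.2-8.3.

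At Grade 2, therefore, nothing requires a hold. After Grade 3 the drugs are already held, so the taper applies if steroids are given.

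The timing can be worked out under these assumptions: a 30-day taper starting *s* days after the last dose, doses due at days 21, 42 and 63, omission counted from the first missed dose, and the ±3-day window ignored.

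- *s* = 0 to 12: *s* + 30 ≤ 42, so dosing resumes on day 42. One dose is missed and 42 − 21 = 21 days are omitted.
- *s* = 13 to 33: *s* + 30 is 43 to 63, so dosing would resume on day 63. That is 63 − 21 = 42 days omitted, more than 28, so Section 8.2 sends the patient to surgery. With at most 4 cycles, 4 − *k* doses are lost after cycle *k*: 3, 2 or 1.

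A restart of both drugs after a steroid-treated Grade 3 event is therefore open only if the taper starts by day 12.

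**5. Number of patients**

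Section 15.17 lists pancreatitis on atezolizumab at 1-10%, with no cause or grade given. In 32 patients, 32 × 0.01 = 0.32 and 32 × 0.10 = 3.2. The chance of at least one case is 1 − 0.99^32 = 27.5% to 1 − 0.90^32 = 96.6%. Grade 2-3 immune-mediated cases are an unstated part of this.

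**6. Effect on pCR**

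Section 16.1112 counts every patient who starts neoadjuvant treatment. One patient moves the estimate by at most 1/32 = 3.1 percentage points.

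**The case against.** The strongest reply is that the pieces already work together. Table 8.22 governs dosing and Section 9.673 governs treatment of the event, so they do not contradict each other, and the row points to Section 9.0. Providers may hold a dose. Appendix III prohibits systemic immunosuppressive drugs during atezolizumab. After Grade 3, the steroids, the taper and the 28-day rule leave little room for a restart at Grade 2, and a patient tapered to 10 mg/day or less would not normally still be at Grade 2 under Section 9.673. Disagreement with the adjuvant table is weak evidence of error, since the two tables differ in both directions. For Grade 3 AST/ALT the adjuvant table is stricter (permanent discontinuation against resumption at Grade 1); for Grade 2 hyperthyroidism the neoadjuvant table is stricter.

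Much of this stands for the Grade 3 restart. It does not settle Grade 2. The cross-reference leads to steroids but not to a hold, and Appendix III separately allows steroids for adverse events without saying that dosing must stop. After Grade 3, the taper does nothing where no steroids are given, and tiragolumab is covered only by the preamble's recommendation. The case also does not depend on the adjuvant table, because the row is the exception within Table 8.22 itself.

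**Conclusion.** The point holds as a safety inconsistency in the dosing rules. Its firm part is Grade 2: the binding table permits both antibodies to continue at a grade where the protocol's own guidance starts high-dose steroids. The Grade 3 restart threshold is out of line (1 of 8 rows), but its practical reach is narrow when steroids are used.

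A reader might infer more than the documents support:

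- *That Table 8.22 orders dosing at Grade 2.* It leaves the choice to the provider.
- *That both drugs would routinely restart at Grade 2 after Grade 3.* The taper and the 28-day rule block most such restarts.
- *That the enzyme-only actions are also wrong because Table 8.3 waits for Grade 1 after a Grade 3 elevation.* Section 9.672 refers and monitors, and only considers steroids if there is no improvement, so a different threshold there is a preference.
- *That 27.5-96.6% is the chance of an affected patient.* It is a loose ceiling covering any cause and grade. It is a ceiling only if tiragolumab does not raise the rate.

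The number of affected patients is unknown. The timing result rests on the 30-day taper and on counting omission from the first missed dose.

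**What to change.** At the next amendment:

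- Add a row to Table 8.22 for immune-mediated pancreatitis. At Grade 2-3, withhold both drugs and resume only at Grade 1 or better after the Section 8.13 taper. Discontinue both on recurrence or at Grade 4.
- Add tiragolumab to the resumption clause of Section 8.13.
- Leave the present actions for enzyme elevation without pancreatitis unchanged.

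The drafting cost is one row and one drug name. The clinical cost falls mainly on a patient newly held at Grade 2. If doses are still due, at least one is missed, because a taper of at least 1 month outlasts a 21-day cycle. If the taper starts after day 12, the patient goes to surgery early and loses all remaining neoadjuvant doses. The patient still counts in the pCR denominator. The doses forgone would have been given under systemic steroids, which Appendix III says may weaken the benefit of atezolizumab. After a steroid-treated Grade 3 event the taper already applies to atezolizumab, so the added cost is mainly any further wait from Grade 2 to Grade 1.
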